Progressive Supervised Home-based Strength Training in Children With Spastic Cerebral Palsy

NCT number: NCT03863197

Protocol data: 1 November 2021

Study protocol

Study outline

A waitlist randomized controlled trial (RCT) will be conducted to define the effects of a progressive resistance training (PRT) program for the knee extensor, knee flexor and plantar flexor muscle groups in children with spastic cerebral palsy (CP). A minimization technique will be used to divide participants in an intervention group, performing a 12-week PRT program and a waitlist control group, continuing usual care for 12 weeks first. After the control period, the participants were offered to participate in the intervention.

Participants

Participants will be recruited across Flanders in Belgium, through the CP reference center of the University Hospitals Leuven, pediatric physiotherapists, and special needs schools. Written informed consent will be obtained from the children's parents or legal guardian prior to the first assessment. The study is registered at Clinicaltrials.gov (NCT03863197) and was approved by local medical ethical committees of University Hospitals Leuven (s59945) and Ghent (EC/2017/0526). The inclusion criteria for participation are 1) a diagnosis of SCP, 2) age at baseline between 5 and 11 years and 3) level of I, II or III on the gross motor function classification system (GMFCS) (Palisano et al., 2008) . Exclusion criteria were 1) botulinum neuro-toxin A injections and/or lower leg casts in the past 6 months, 2) lower limb bony surgery in the past 2 years, 3) lower limb muscular surgery or selective dorsal rhizotomy at any time point, 4) inability to communicate in Dutch or English and 5) inability to understand instructions and cooperate during assessments and training.

For comparison of baseline data, a convenience sample of typically developing (TD) children will be recruited via hospital co-workers and students within the same age range of 5–12 years. The TD children could not have any known neurological or orthopedic lower limb problems. The TD children will only participate in one assessment of isometric strength, 3D freehand ultrasonography and functional strength (see below).

Study design

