Age, body mass and height will be recorded for the participants at each assessment. Usual care and treatment history will be recorded at the PRE-assessment using standardized in-house questionnaires. A routine clinical examination regarding the investigated muscle groups will be performed, including passive joint range of motion, spasticity, manual muscle strength and selective motor control (SMC), based on standard clinical scales (Bohannon & Smith, 1987; Boyd, 1999; Gage et al., 2009; Matthews, 1977). These clinical examination parameters will be used to define the most affected leg for bilaterally affected children. If both sides are equally affected, the right leg will be used. Lower limb SMC will be assessed with the selective control assessment of the lower extremity total limb score (Fowler et al., 2009). Assessments will be performed in the same order, starting with clinical examination and muscle morphology, followed by isometric and functional strength and lastly gross motor function and walking capacity.

2. Isometric strength assessments

Knee extensor, knee flexor and plantar flexion maximum voluntary isometric contractions were collected with a fixed dynamometer in a previously described, custom-designed chair (Goudriaan et al., 2018). The dynamometer is positioned at 75% of the lower leg and foot length, and the level arm distance is measured between this position and the joint axis. After a test trial, we aim to collect 3 well executed maximum voluntary isometric contractions with a duration of 3 to 5 seconds. Standardized verbal encouragement and visual feedback will be provided throughout the isometric contraction. The protocol includes periods of rests of at least 10 seconds between repeated

assessments and of at least 2 minutes between different muscle groups. Peak force is extracted from each trial with a custom-written MATLAB script and maximal joint torque (in Nm) will be calculated by multiplying peak force with the lever arm and taking the average of the 3 trials. Knee and plantar flexion maximal voluntary isometric contractions are corrected for gravity by subtracting the gravitational torque in rest from the outcomes. Maximal joint torque will be normalized by dividing it by body weight (Nm/kg).

3. Three-dimensional freehand ultrasonography

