A previously validated 3-dimensional freehand ultrasonography technique will be used to evaluate muscle morphology, combining a 2-dimensional B-mode ultrasonography device (Telemed-Echoblastar 128 Ext-1Z, with a 5.9 cm 10MHz linear ultrasound transducer, Telemed, Ltd, Lithuania) with a motion tracking system (Optitrack V120:Trio, NaturalPoint, Inc, Corvallis, Oregon, USA) (Cenni et al., 2016). Ultrasound settings will be kept constant throughout the study period, at a frequency of 8MHz, with a focus of 3cm, a gain of 64%, a dynamic range of 56 dB and unaltered time-gain compensation. Depth can vary between 5cm and 7cm, adjusted to muscle size. The m. rectus femoris and m. tibialis anterior will be scanned in supine position with a triangular cushion underneath the calf, providing approximately 25 degrees of knee and hip flexion. The m. semitendinosus and m. medial gastrocnemius will be scanned in prone position with a triangular cushion underneath the shank, providing 25 degrees of knee flexion and an unconstrained ankle angle. STRADWIN software (version 6.0; Mechanical Engineering, Cambridge University, Cambridge, UK) will be used for data acquisition, generation of 3-D datasets, and data processing. Data processing will be performed by experienced processors, drawing equally spaced transverse plane segmentations throughout the 3-D datasets, which will be interpolated with an automatic cubic planimetry technique resulting in the muscle volume (in mL) (Treece et al., 1999). Muscle length (in mm) will be defined by calculating the linear distance between muscle origin and muscle tendon junction. Both muscle volume and muscle length will be normalized to fibula length to correct for skeletal growth (mL/cm and cm/cm). The echo-intensity (EI) from ultrasound images will be used as an indication of intrinsic muscle quality, with higher EI-values representing an increased ratio of non-contractile vs. contractile tissue (Pitcher et al., 2015; Young et al., 2015). EI (expressed in arbitrary units) will be computed as the average value throughout the interpolated reconstruction of the muscle.

4. Functional strength assessments

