Endurance functional strength will be assessed with 30-s repetition maximum tests including bi- and unilateral heel raise, sit-to-stand, and lateral step-up, as previously described (van Tittelboom et al., 2021). Participants completed as many repetitions as possible in 30 seconds. Each test will be 3 times and the average taken as final score. Explosive strength will be evaluated with a standing long jump, with both feet together, which will also be repeated 3 times and the scores averaged. The use of orthoses will not be allowed, as the PRT program will also be performed without orthoses.

5. Gross motor function and walking capacity

Gross motor function will be evaluated with the Gross Motor Function Measure-Item Set (Brunton & Bartlett, 2011) and the Gross Motor Ability Estimator 2 used to estimate the final score. The 1-minute walk test, performed on an indoor 20-m track, will be used to assess walking capacity (Chrysagis et al., 2014; McDowell et al., 2009). The participant will be instructed to walk as fast as possible without running and the distance covered in 1 minute will be recorded. Both assessments will be performed without orthoses, but a key-walker is allowed for the 1-minute walk test for children classified as GMFCS-level III.

6. Statistics

Descriptive statistics for all groups will be summarized using appropriate summary indices. The comparison between TD children and children with CP will be performed with a Student's *t*-test (after confirming equality of variances) or the Mann-Whitney *U*-test. Associations between muscle morphology measures, muscle strength and participant characteristics will be evaluated with univariate linear regressions followed by a multivariate linear regression using a backward approach. The linear regressions in the TD cohort based on an anthropometric variable will be used to define the deficits in muscle strength and muscle morphology in CP children.

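### The comparison of children with CP with typically developing (TD) children is not adjusted for age, which leaves chiefly functional strength open to age confounding; the two stated age ranges also need reconciling

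*Combined protocol and SAP*

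**What the plan says.** The test is set in section 6 (Statistics): "The comparison between TD children and children with CP will be performed with a Student's" t-test if variances are equal, otherwise a Mann-Whitney U-test. No covariate, matching or stratification is mentioned.

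On the TD sample, the Participants section says: "For comparison of baseline data, a convenience sample of typically developing (TD) children will be recruited via hospital co-workers and students", and places them "within the same age range of 5–12 years". The CP inclusion criterion in the same section is "age at baseline between 5 and 11 years".

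The outcomes available in both groups are given there too: "The TD children will only participate in one assessment of isometric strength, 3D freehand ultrasonography and functional strength". Their scaling differs:
- Isometric torque is divided by body weight (section 2).
- For morphology, "Both muscle volume and muscle length will be normalized to fibula length to correct for skeletal growth", giving mL/cm for volume and cm/cm for length (section 3).
- Echo-intensity is an average grey value with no stated normalisation (section 3).
- The 30-second repetition tests and the standing long jump are raw averages of three trials (section 4).

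Separately, section 6 uses linear regressions in the TD cohort on an unnamed anthropometric variable to define CP deficits in muscle strength and muscle morphology. Adjustment for age is specified only for the mixed models that compare the intervention and control groups.

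**The concern.** CP and TD children are not randomised to their groups, so nothing in the design makes their ages comparable. If the mean ages differ, a two-sample test attributes to CP whatever part of the difference is due to age. The error can go either way: older TD children exaggerate a CP deficit and younger ones hide it. Even with equal mean ages, age variation stays in the error term and costs power.

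The plan treats age and growth as relevant elsewhere. It minimises on age, adjusts the randomised comparison for age, and scales muscle size for skeletal growth. The one non-randomised group comparison has no age term. Functional strength is the most exposed: it has no stated normalisation, it is not clearly within the regression-based deficits, and section 6 identifies it as the largest set of parameters (five).

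**Working it through.** **The plan's own figure.** The Sample size section gives 39 independent observations per group (d = 0.8, level 0.01, power 80%). This reproduces with a two-sided noncentral-t calculation: power is 79.8% at 38 and 81.0% at 39. The design effect is 1 + 0.1 × (2 − 1) = 1.1; 39 × 1.1 = 42.9, so 43 legs; 43/2 rounds up to 22 children per group. These figures size the randomised comparison. No sample size is given for CP versus TD.

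**Age windows.** Read as exact ages with uniform distributions, the mean ages are (5 + 11)/2 = 8.0 and (5 + 12)/2 = 8.5 years, a gap of 0.5 year. If 5–11 means completed years, it runs to the 12th birthday, the two windows coincide and the gap is zero. The documents do not say which is meant.

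**What normalisation removes.** Suppose all lengths grow by a factor k (an assumption).
- Volume per fibula length scales as k³/k = k², so it still rises with size: at k = 1.1 it rises by 21%.
- Muscle length per fibula length scales as k/k = 1.
- Torque (force k² times lever arm k) per body weight (k³) also scales as 1.

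The last two are therefore better protected, although no ratio guarantees independence from age.

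**Size of the bias.** Assumed, not in the documents: age SD 1.9 years; 44 CP children (2 × 22) and 30 TD children, one value each; two-sided level 0.01; no true difference; r is the outcome-age correlation that remains after any normalisation.

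- Bias in SD units = r × gap / 1.9
- Noncentrality = bias × √(44 × 30 / 74) = bias × 4.22
- Critical value on 72 degrees of freedom = 2.646

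| Age gap (years) | r | Bias (SD) | False-positive rate, t-test |
|---|---|---|---|
| 0 | any | 0 | 1.0% |
| 0.5 | 0.3 | 0.08 | 1.4% |
| 0.5 | 0.5 | 0.13 | 2.2% |
| 0.5 | 0.7 | 0.18 | 3.5% |
| 1.0 | 0.3 | 0.16 | 2.8% |
| 1.0 | 0.5 | 0.26 | 6.8% |
| 1.0 | 0.7 | 0.37 | 14.6% |

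In simulation of the one-year gap, a linear model with age holds the rate at about 1%. With 44 children per group and age SD 2.0, the unadjusted rates at a one-year gap are similar: 3%, 8% and 17% for r = 0.3, 0.5 and 0.7.

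**Masking.** Take a true deficit of 0.5 SD and TD children one year younger. The expected unadjusted difference is 0.5 minus the bias: 0.34, 0.24 and 0.13 SD for r = 0.3, 0.5 and 0.7. Power is then 12%, 6% and 2%, against roughly 30%, 40% and 60% with age in the model (simulation).

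**Precision alone.** With no age gap, age adjustment multiplies the residual variance by 1 − r² = 0.91, 0.75 or 0.51. For the same 0.5 SD deficit, unadjusted power is about 30%; adjusted power is roughly one third, 40% and 60%.

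**The case against.** A reader might infer that most outcomes depend on age, that the two groups do differ in age, and that the plan will in general read that difference as a CP deficit. The documents support none of these.

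- **Age dependence.** It is stated nowhere. What matters is dependence after normalisation, and torque per kg and length per fibula length already remove body size in large part.
- **Deficits.** For strength and morphology they are defined from TD regressions on an anthropometric variable, not from the two-sample test.
- **Imbalance.** None is shown. The text intends one age range, and the two windows may be identical. Under the assumptions above, the standard error of the mean age difference is 1.9 × √(1/44 + 1/30) = 0.45 year. A one-year gap would thus be 2.2 standard errors out under random sampling from one window. Larger gaps, which would give much higher error rates, have no basis in the documents.
- **The null scenario.** The stated aim is to define deficits, so a false positive under exactly no difference is not the main risk.
- **Importance.** This is an ancillary baseline comparison. The randomised effect uses no TD data and its models adjust for age. Descriptive statistics for all groups could also reveal an imbalance.

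These objections narrow the point and most of them stand. They do not remove it. A convenience sample can be systematically older or younger, so the random-sampling argument gives limited comfort. The regression sentence does not clearly reach functional strength or echo-intensity. Seeing an imbalance in a descriptive table does not correct the test.

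**Conclusion.** The point holds in a limited form. The CP–TD test is unadjusted, its reference group is an unmatched convenience sample, and the two age ranges as written do not agree. Exposure to confounding is greatest for functional strength, possible for echo-intensity, and partial for muscle volume in mL/cm.

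Under the stated assumptions (age SD, TD number, gap and correlation are all outside the documents), the bias is about 0.08 to 0.37 SD, and the false-positive rate about 1.4% to 15% against a nominal 1%. If ages turn out balanced, the bias is zero and only precision is lost. The calculations are for the t-test; the rank test is equally unadjusted but was not evaluated. No figure stated in the plan changes, and conclusions on the training effect are untouched. The change is worth making because it costs little and removes reliance on chance balance.

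**What to change.** 1. Replace the two-sample test in section 6 by a linear model of each outcome on group and continuous age. Add sex only if it is recorded; section 1 names age, body mass and height, not sex.
2. Check the group-by-age interaction. If the slopes differ, report the group difference at stated ages rather than as one coefficient.
3. State what replaces the rank test when residuals are clearly non-normal, for example a transformation or robust standard errors.
4. Reconcile the 5–11 and 5–12 year ranges, or restrict this comparison to the common window.
5. Name the anthropometric variable in the TD regressions, and say whether functional strength and echo-intensity fall under the deficit definition.

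The cost is SAP wording, a common-slope assumption to check, and possibly a few TD children left out of this comparison. Age is already recorded for participants at each assessment; the plan should say explicitly that this includes TD children. The planned software can fit the model.

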After enrollment and prior to the first assessment, participants will be assigned to the intervention or the control group through randomization by minimization. MinimPy will be used to randomize the participants based on age (2 levels: <8 years and >8 years) and GMFCS score (3 levels: I, II and III) (Saghaei, 2011). The allocation ratio will be 1:1 with probability set at 0.75. The biased coin minimization will be used as probability method and marginal balance as distance measure.

Assessments are planned in the University Hospitals and special needs schools, at baseline (PRE) and after the 12-week control or intervention period (POST). Training and assessments will always be

conducted on different days. Participants in the intervention group start training within 2 weeks after the baseline assessment. For both groups, the POST assessments will be performed within 1 week after the 12-week period. Blinding is not completely possible since participants and trainers are aware of group allocation. Assessors are also aware of group allocation during assessments but data will be anonymized before processing and analyses. The participants will be assessed by the same assessors (PRE and POST) and the data of one participant will be processed by the same processor.

Piloting for the feasibility of the measurements and parameter extraction was done through prior and parallel investigations. The exercises used during the training were piloted through iterations with strength and conditioning specialists to ensure correct exercise selection and also with senior pediatric physiotherapists and their patients to ensure the applicability in targeted population of children with SCP.

Sample size

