At the moment of trial design (2018), no data were available on an RCT investigating changes in muscle size after PRT in a population of children with SCP. Therefore, effect sizes (d) of systematic reviews and meta-analyses reporting muscle strength outcomes after PRT were used. Reported effect sizes were moderate ($d=0.53$) (Ryan et al., 2017) and large ($d=1.050$ and $d=1.105$) (Park & Kim, 2014). Based on a large effect size of $d=0.8$ with the probability of making a type I error set equal to or less than 1% ($p\leq 0.01$) and a power of 80%, an independent samples t-test with common standard deviation required 39 independent observations per group to compare the evolution over time between the intervention and control groups. To account for the possibility of clustered legs in bilaterally affected participants a design effect (Killip et al., 2004) was calculated resulting in an estimated sample size of clustered observations per group with following formulas:

$$\text{Design effect} = 1 + \rho * (m-1),$$

where ρ is the intraclass correlation and m the cluster size, and,

$$\text{Estimated sample size of clustered legs} = \text{estimated sample size of independent observations} * \text{design effect} = m * \text{number of participants}$$

With a cluster size of $m=2$ (2 legs per bilaterally affected participant) and an intraclass correlation coefficient of $\rho=0.1$, based on literature of general health parameters (Adams et al., 2004), the estimated design effect was 1.1, resulting in 43 clustered legs, or 22 bilaterally affected participants per group. A group including both uni- and bilaterally affected children would require a sample size between 39 and 43.

Intervention

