To define the effects of the PRT intervention linear mixed models will be applied to evaluate the difference in evolution over time between the control and intervention group (time*group interaction effect) and between PRE and POST within each group (time effect). The random effects in these models can correct for the correlation between repeated observations within the same subject. Moreover, in the case of missing values that are completely at random, i.e. not related to any observed or unobserved outcomes, or at random, i.e. related to observed outcomes, linear mixed models provide valid inferences for missing observations. A covariance structure for repeated measurements to model longitudinal dependencies within the participant will be applied with a random intercept for participant (legs are nested within participants). The models will be adjusted for age and GMFCS level as covariates as these were used to allocate the children to the control or intervention group. Age was entered as a categorical variable (<8 years and >8 years). A full-factorial time*group mean model adjusted for age and GMFCS level, with a compound symmetry covariance matrix, unless an unstructured covariance matrix results in a better fit (Akaike information criterion decrease of >2). Adjustment for age (categorical variable: <8 years and >8 years) and GMFCS level will be included as these were used to allocate the children to the control or intervention group.

The α -level will be adjusted to $p \leq 0.01$ since multiple parameters are evaluated for most research questions, with a maximum of 5 parameters (functional strength). All analyses will be performed with SPSS (Version 28, SPSS Inc., Chicago, Illinois).

Finally, the data of the total intervention group (intervention + waitlist control group with delayed intervention) will be used to define the association between baseline properties and the changes in the outcome parameters after PRT with uni- or multivariate regression (mixed) models.

References

<https://doi.org/10.1016/j.jclinepi.2003.12.013>

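### The CP-TD comparison names only Student's t-test and Mann-Whitney, with equal variances as the sole stated condition; read as a location test, this does not hold its level when both spread and group size differ.

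*Combined protocol and SAP*

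**What the plan says.** Section 6, Statistics, specifies the baseline CP-TD comparison in one sentence: a Student's t-test ("after confirming equality of variances) or the Mann-Whitney" U-test. It names no variance test or cut-off, no normality criterion and no Welch test. It also does not say which hypothesis Mann-Whitney is meant to address.

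The same section sets the significance level: "The α -level will be adjusted to $p \leq 0.01$ since multiple parameters are evaluated for most research questions". It names the software: "All analyses will be performed with SPSS (Version 28, SPSS Inc., Chicago, Illinois").

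The Participants section describes the comparison group as "a convenience sample of typically developing (TD) children will be recruited via hospital co-workers and students" and gives no target number. The 1:1 ratio in Study design ("The allocation ratio will be 1:1 with probability set at 0.75") concerns the two trial arms only, so nothing in the plan makes the CP and TD groups equal in size.

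**The concern.** Mann-Whitney is a natural stand-in for a t-test when data are not normal. It is not a remedy for unequal variances. Its reference distribution assumes that the two distributions are identical. If the centres agree but the spreads differ, the variance it assumes for its own statistic is wrong. It then rejects too often when the smaller group is the more variable one, and too rarely when the smaller group is the less variable one.

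The conditions for this are plausible here. The CP group spans GMFCS levels I to III, while the TD group is healthy and of unstated size. At stake is the accuracy of the p-values for CP-TD differences in strength, muscle morphology and functional strength, at a level that the plan tightened to 0.01 because of multiplicity.

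**Working it through.** **1. Size of the CP group.** The plan gives no sample size for the CP-TD comparison, so the CP number has to come from the trial's own calculation. Its inputs are "Based on a large effect size of $d=0.8$ with the probability of making a type I error set equal to or less than 1"%, and the stated result is "a power of 80%, an independent samples t-test with common standard deviation required 39 independent observations per group".
- Normal approximation: n = 2(2.576 + 0.842)² / 0.8² = 36.5, so 37. The noncentral-t calculation gives 38.19, so 39. The plan's figure is reproduced (two-sided).
- Design effect: 1 + 0.1 × (2 − 1) = 1.1, and 39 × 1.1 = 42.9, matching the plan: "resulting in 43 clustered legs, or 22 bilaterally affected participants per group".
- Total CP children: 2 × 22 = 44 if all are bilaterally affected, up to 2 × 39 = 78 if all observations are independent. The value 44 used below is the low end.

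**2. Assumptions.** TD size (20, 44 or 88) and SD ratio (1.5 or 2, either way) are assumed. So are normal data with equal means, a two-sided level of 1%, and a mean-centred Levene test at 5% as the variance check.

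**3. Mann-Whitney by formula.** Take the proportion of CP-TD pairs in which the TD value is higher. With equal normal means its large-sample variance is

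V = v_C/n_C + v_T/n_T, where each v = arcsin(own variance / sum of the two variances) / (2π).

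Mann-Whitney assumes V0 = (1/n_C + 1/n_T)/12. These agree when variances are equal, since arcsin(0.5)/(2π) = 1/12. The true level is 2[1 − Φ(2.576 × √(V0/V))].

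At SD ratio 2, v = arcsin(0.8)/(2π) = 0.1476 for the more variable group and arcsin(0.2)/(2π) = 0.0320 for the other.
- 44 (SD 1) v 20 (SD 2): V = 0.00073 + 0.00738 = 0.00811; V0 = 0.00606; ratio 1.338; z = 2.227; level 2.6%.
- 44 (SD 2) v 20 (SD 1): V = 0.00335 + 0.00160 = 0.00496 (from unrounded terms); V0 = 0.00606; ratio 0.818; z = 2.848; level 0.4%.
- 44 (SD 2) v 88 (SD 1): V = 0.00335 + 0.00036 = 0.00372 (unrounded terms); V0 = 0.00284; ratio 1.309; z = 2.251; level 2.4%.
- 44 v 44: V = 0.00335 + 0.00073 = 0.00408; V0 = 0.00379; ratio 1.078; z = 2.481; level 1.3%.

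**4. The whole rule by simulation.** The rule applies Levene first, then Student if it is not rejected and Mann-Whitney otherwise. With 20,000 to 40,000 runs per cell, repeated runs differ by 0.1 to 0.3 points. True error at nominal 1%:

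| CP v TD | Rule | Welch |
|---|---|---|
| 44 (SD 1) v 20 (SD 2) | 2.6% | 1.0% |
| 44 (SD 2) v 20 (SD 1) | 0.3% | 0.9% |
| 44 (SD 2) v 88 (SD 1) | 2.4% | 1.0% |
| 44 (SD 1) v 88 (SD 2) | 0.5% | 1.0% |
| 44 (SD 1) v 20 (SD 1.5) | 2.1% | 1.0% |
| 44 (SD 1.5) v 20 (SD 1) | 0.5% | 1.0% |
| 44 v 44, SD ratio 1.5 | 1.1% | 1.0% |
| 44 v 44, SD ratio 2 | 1.3% | 1.0% |

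At nominal 5%, the first two cells give 9.3% and 2.6%. At the high end of the CP range, 78 v 20 with SD ratio 2 gives 3.6% or 0.2% at nominal 1%.

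**5. Where the excess comes from.** At 44 v 20 with the smaller group 1.5 times as variable, Mann-Whitney alone gives 1.8%, the rule 2.1% and Student alone 2.7%. In this cell the variance test fails to reject in about half of the samples, and Student's test is then used on unequal variances. So at mild ratios part of the excess belongs to Student's test.

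**The case against.** Four points can be made for the plan.

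**The trigger is not spelled out.** The parenthesis qualifies the t-test only, and there is no otherwise-clause. Non-normality is an ordinary reason to use Mann-Whitney, and the outcomes include 30-second repetition counts. A reader might infer that the plan expressly prescribes Mann-Whitney for unequal variances. It does not; that is only the literal consequence of the one condition given. This stands. Yet on the normality reading the plan has no method at all for normal data with unequal variances, so the sentence needs work either way.

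**Mann-Whitney is not invalid in itself.** It holds its level for the hypothesis of identical distributions and can be reported as a comparison of stochastic ordering. This also stands. The fault applies to a location reading, which is the natural one for a substitute for a t-test but is not stated.

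**The error need not be material.** A reader might infer that the error rate is wrong whatever the data look like. The documents do not support this, because they give neither the TD number nor any SD. With equal groups and symmetric data the error is upward only and small.

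**The pre-test is not shown to do harm of its own.** A reader might object to the variance check simply because it makes the choice of test depend on the data. With equal variances at 44 v 20 the rule rejects in 0.9% of samples at nominal 1%. The damage arises from what follows the check when variances differ.

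**Conclusion.** The point holds in a limited form. As a location test, the CP-TD rule exceeds or falls short of its nominal 1% when variances and group sizes both differ. At SD ratio 2 with the sizes above, the range is roughly a quarter to two and a half times nominal. The direction cannot be fixed from the documents, since it depends on which group proves smaller and which more variable. The figures rest on the assumed TD sizes, SD ratios, normality and Levene cut-off, and on 44 CP children.

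No inference about the training effect follows. The randomised comparison uses linear mixed models, and the figure of 39 per group does not depend on this rule. CP deficits are to be derived from TD regressions, not from this test. What is affected is a single baseline comparison with a convenience sample, so the change is desirable rather than necessary.

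**What to change.** In section 6, Statistics, replace the sentence on the CP-TD test with Welch's t-test for these comparisons, without a preliminary variance test. For clearly skewed outcomes, specify one of two routes: transform or bootstrap the mean difference, or keep Mann-Whitney and state its hypothesis as stochastic ordering. The skewed case needs its own line because Welch is not exact there: with moderately skewed simulated data (gamma, shape 4) its error was 0.9% to 1.8% at nominal 1%.

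The cost is small. SPSS already prints the unequal-variance row of the t-test. With equal variances, d = 0.8 and a 1% level, simulated power is 86.3% for both Student and Welch at 44 v 44. At 44 v 20 it is 62.2% for Student and 59.9% for Welch, a loss of 62.2 − 59.9 = 2.3 points.
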